- 6.E.4. Visits 2c-11 (Treatment and End-of-Treatment Visits): Patients will first receive counseling and study medication during a treatment session (visit 2c) scheduled on the same day as the baseline assessment. Patients will be given study medication consisting of ZNS or matching PLC and titrated up to a maximum of 600 mg/day of ZNS (see Table 1). We will use blocked stratified randomization with treatment site (Yale versus UCHC) and use of antidepressants/psychotropic (yes/no) as the stratification variables, and block sizes of 4 in each stratum to achieve treatment balance throughout the randomization process. During the 16-week treatment period, patients will come in for a visit within 1 week after starting the study medication (week 1). They will then come in on weeks 3, 5, 7, 9, 11,13, and 16. After completing a two-week taper, patients will return on week 18. (Note: a research staff member will call the patient on weeks 2, 4, 6, 8, 10, 12, 14, 15, and 17. The purpose of this call will be to check in with the patient and make sure they do not have any questions and that they are tolerating the medication.) At each visit, the patient's breath alcohol level (BAL), weight, and vital signs will be measured. Participants will be expected to have a BAL under the legal limit (.08) in order to participate in visits. At screening, all female subjects will have a blood pregnancy hCG quantitative titer drawn to detect pregnancy. Urine samples will be collected at each visit for drug screening and once monthly for female subject's pregnancy testing. Samples for ETG (urine) and PEth (blood) will be collected as indicated in Table 2. Patients will then complete questionnaires and be interviewed by the study nurse about their concomitant medications, adverse events, and protocol compliance. At every treatment visit (i.e., for a total of 9 sessions), the nurse will deliver the MM intervention. At midpoint, Week 9, Baseline impulsivity will also be measured before imagery using the Barrett Impulsivity Scale [51]. At the end of treatment, the research assessment will be repeated, including a guery of the patient's belief as to their treatment condition (using the Medication Questionnaire; MED-Q). Blood samples for measurement of serum GGTP will be obtained to assess the validity of self-reported drinking. All patients will be asked to complete an end-of-treatment evaluation and to complete all scheduled assessments to facilitate intent-to-treat (ITT) analyses. Participants who discontinue the medication before the typical Endpoint will be given the option to participate in an abbreviated version of the visits starting at what would normally be the visit labeled Week 16 onward. This will also allow us to monitor them for safety while tapering (if needed).

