6.I. Other Treatments Allowed During the Study: Subjects will be allowed to continue to receive, or will be referred for, additional psychiatric care as needed. This is similar to what has been done in previous studies in this population. They can receive antidepressants and other medications, as long as the medication is not on the list of those excluded. The type and amount of services received will be collected as data. Subjects will be allowed to participate in twelve step programs, group psychotherapy, day treatment programs etc.

6.J. STRESS REACTIVITY LAB PROCEDURES: (Visit 2b)

Intake: Qualified staff will meet with eligible subjects to explain all study procedures and risk/benefits and obtain informed consent. Next, scripts for the imagery procedures will be developed and audio recorded on the day of the lab, or after screening but before the day of the lab. The stress reactivity lab session is performed twice, the first stress reactivity lab session occurs after screening but prior to starting medication. The second stress reactivity lab session occurs after being on the target dose for at least 2 weeks (i.e. between weeks 9-16) Each stress reactivity lab takes place on one day, and is approximately 4 hours long. A description of the procedure is provided in Table 3.

6.J.1. *Imagery Script Development*: First, scripts for the guided imagery induction will be developed. The *stress imagery script* will be based on subjects' description of a recent personal stressful event that is self-rated as an 8 or above on a 10-point Likert scale, where 1 = "not at all stressful" and 10 = "the most stress I have recently felt in my life". Examples of acceptable stressful situations include breakup with significant other, a verbal argument with a significant other or family member or unemployment-related stress, such as being fired or laid off from work. A *neutral-relaxing script* will be developed from the subjects' commonly experienced neutral-relaxing situations. Neutral-relaxing events that involve nicotine or alcohol/drugs will not be allowed. An *alcohol craving cue imagery script* will be based on subjects' description of a recent event in which alcohol was consumed. Stressful situations will not be acceptable for these latter two types of scripts.

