- **6.K.1. Procedures:** Procedures for the monitoring and analysis of data were developed during previous clinical trials conducted at Yale and will be overseen by Drs. [name] and [name].
- 6.K.1.a. To Examine the Efficacy of ZNS (Specific Aim 1), Primary Outcome: We will use *drinks per week* as the primary outcome variable. This is also the primary outcome we are using for veteran ZNS study, and is one that can be readily applied when combining the samples. Recently the NIAAA and FDA Alcohol Clinical Trials Initiative (ACTIVE: a workgroup of experts in the field tasked with optimizing alcoholism clinical trials outcomes and methods) has suggested that for medication development trials and small to medium size trials, continuous outcome variables such as drinks/week or heavy drinking days per week are optimal as opposed to categorical outcomes. We will use a mixed models approach to examine for a statistically significant difference in drinks per week and on continuous secondary outcome variables. The model will include fixed effects for medication group, week, and the interaction between medication and week. We will include pre-treatment drinking behavior (past month HDD) as a covariate and will select the best-fitting variance-covariance structure based on Schwartz-Bayesian Information criterion (BIC). We will incorporate a grace period corresponding to the time it takes to titrate the medication to target dose into the models, and we will focus the primary analysis on the last 8 weeks of treatment at the target dose. All of these outcomes can be obtained from the TLFB data, and from the daily drinking data obtained from the IVR.

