An important initial consideration in considering efficacy will be to identify baseline differences between groups that may have occurred despite randomization. A successful outcome during the treatment trial will be defined in terms of a statistically significant difference on the primary outcome measure: drinks per week, compared during the 8 weeks of active treatment at the target dose, allowing for an 8 week grace period for the medication titration. For all analyses, heavy drinking days will be defined as follows; for men > 4 drinks in a day and for women > 3 drinks in a day. Patients will be followed irrespective of whether they continue to receive medication treatment, so that analysis will include all data available for the 8-week treatment period. All analyses will be **intent-to-treat**. The α will be set at .05 for the primary outcome variable. Between site differences will be explored. We will test interaction effects of GRPS in the regression models for the primary/secondary outcomes (**Exploratory Aim 1**), testing the hypothesis that ZNS's effect on drinking is greater in those with higher GRPS.

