6.K.2 Secondary outcome measures: We will use a mixed models approach to examine for a statistically significant difference on heavy drinking days (HDD) per week, changes in GGTP level, measures of alcohol urge/craving (AUQ), and alcohol-related problems (as measured on the SIP). For each of these outcome measures, the model will include fixed effects for medication group, week, and the interaction between medication and week. We will include pre-treatment drinking behavior (past month HDD) as a covariate and will select the best-fitting variance-covariance structure based on Schwartz-Bayesian Information criterion (BIC). We will incorporate a grace period corresponding to the time it takes to titrate the medication to target dose into the models, and we will focus the primary analysis on the 8 weeks of treatment at the target dose. We will use the Hommel's correction for multiple comparisons on the secondary outcomes to guard against chance findings. With last secondary outcome measure percentage of subjects with no heavy drinking days (PSNHDD), we will use a logistic regression analysis with PSNHDD as a categorical dependent variable. Medication condition (PLC or ZNS) will be the main independent variable, and we will include the variables of civilian or veteran status. and sex as covariates. We will also examine the use of biomarkers (GGT, PEth) to verify and adjust subjective drinking data as these biomarkers can detect occult harmful drinking when a subject is not forthcoming.

6. K. 3. Dropouts and missing data: For the analysis of PSNHDD using logistic regression, all dropouts will be counted as relapsed. For all repeated measures analysis, we will use all V.6 05Jun2020

available data on individuals and thus dropouts provide data until the point of dropout. We will compare dropout patterns between groups and if there are concerns of informative dropout and/or informative intermittent missing data, we will use pattern mixture models [98] to perform sensitivity analyses to our main analyses. Adherence to the medication will be evaluated and controlled for in secondary analyses. We will evaluate and compare both medication conditions (PLC, ZNS) for percentage of prescribed pills taken.

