- **6.K. 6. Safety:** Safety will be analyzed using categorical outcomes, defined by the type and severity of adverse effects. Summary measures of adverse events will be developed by organ system from the SAFTEE [77, 78] and will be compared for patients receiving ZNS or PLC using \Box^2 analysis or Fisher's exact tests, with an emphasis on moderate-to-severe adverse events.
- 6. K. 7. Sample Size And Power Estimate (Specific Aim 1): For continuous outcomes, based on the effect sizes from our pilot study of ZNS (showing a moderate effect size on drinks/week d=0.5, and .27 HDD/week), we estimated that a study with N=128 subjects (a 20% drop out rate) would be well powered (>.80) to detect a medium effect size difference on the secondary outcomes HDD per week and total drinks per week for the main effect of group assuming alpha level of 0.05. Based on past trials we are expecting a dropout rate < 30%. We will quantitatively examine the veteran and civilian populations for differences in variance and treatment response, and combine them (if valid) in a patient-level pooled analysis, further increasing power on all outcomes. If substantial differences are observed between the veteran and civilian samples, we will meta-analyze them. For PSNHDD, from the pilot study, in the ZNS group, 12 of 20 subjects did not relapse in the 28 days of the study, compared to 7 of 20 PLC subjects. Using this effect size, the proposed sample size of 80 subjects per group has >89% power to detect such a difference in the rates of no heavy drinking (i.e. 60% vs. 35%), assuming a two-sided alpha level of 0.05. We can also detect slightly smaller differences (60% vs. 38%, 35% vs. 57%) with 80% power under the same assumptions. Both in the estimation of effect

size from the pilot data and in the sample size analysis, dropouts are counted as relapsed to heavy drinking.

6 K. 8. Pharmacogenomic and Micro-longitudinal analyses power estimate (Aim 2, exploratory aims): There is little ZNS-specific data by which we could reasonably estimate effect sizes for these analyses. Three recent treatment studies by our group showed significant pharmacogenetic effects with samples of about 110-150 in each [15, 85, 102]. By using a mixed models approach on drinking variables, and HLM for the micro-longitudinal analyses, we will be adequately powered to detect medium-to-large effects in these analyses.

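### Randomisation is stratified by site and antidepressant/psychotropic use, but neither factor is in the primary or continuous secondary models; the cost is a slightly conservative test if the strata are prognostic

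*Combined protocol and SAP*

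**What the plan says.** Section 6.E.4 sets out "blocked stratified randomization with treatment site (Yale versus UCHC) and use of antidepressants/psychotropic (yes/no) as the stratification variables", with blocks of 4 in each stratum.

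For the primary outcome, drinks per week, Section 6.K.1.a says: "The model will include fixed effects for medication group, week, and the interaction between medication and week". It adds: "We will include pre-treatment drinking behavior (past month HDD) as a covariate". On site, the same section says only: "Between site differences will be explored".

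For the continuous secondary outcomes, Section 6.K.2 repeats the structure: "For each of these outcome measures, the model will include fixed effects for medication group, week, and the interaction between medication and week", again with past-month HDD as covariate. For the percentage of subjects with no heavy drinking days (PSNHDD) it plans a logistic regression: "Medication condition (PLC or ZNS) will be the main independent variable", with civilian/veteran status and sex as covariates.

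Antidepressant/psychotropic use does not appear in the statistical section (6.K). It will vary between participants, since Section 6.I says of them: "They can receive antidepressants and other medications, as long as the medication is not on the list of those excluded".

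**The concern.** Stratified blocks make the arms more alike on site and psychotropic use than simple randomisation would. If those factors predict drinking, the true sampling variance of the treatment difference falls. A model without them leaves their variance in the error term, so its standard error is too large for the design. The test then rejects less often than its nominal level and loses some power.

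The margin is thin. For drinks per week the plan claims power just over 0.80 at N = 128, and Section 6.K.7 expects dropout only to stay below 30%. Both factors must be known in order to randomise, so the analysis would be forgoing information already in hand.

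**Working it through.** **Inputs from the documents.** 80 per arm (Specific Aim 1); N = 128 after 20% dropout, so 64 per arm; dropout expected below 30%, so at worst 160 × 0.7 = 112, or 56 per arm; d = 0.5 for drinks per week and 0.27 for HDD per week; PSNHDD 60% versus 35% (all Section 6.K.7); α = 0.05, taken as two-sided. Section 6.K.7 does not say whether 0.27 is standardised; it is read so here.

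**Assumption not in the documents.** R² is the share of outcome variance left after past-month HDD that the two strata explain, taken as 0 to 10%.

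**Step 1: reproduce the plan's power.** With nc = d√(n/2), 64 per arm and d = 0.5 give nc = 0.5 × √32 = 2.828 and power Φ(2.828 − 1.96) = 0.807 (0.801 by noncentral t), against the stated >0.80. For PSNHDD, 60% versus 35% at 80 per arm gives 0.894, against the stated >89%. Both agree.

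**Step 2: with and without the strata.** Under stratified randomisation:

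- strata omitted: power = Φ((nc − 1.96)/√(1 − R²)); type I error = 2Φ(−1.96/√(1 − R²))
- strata included: power = Φ(nc/√(1 − R²) − 1.96); type I error stays at 0.05

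Drinks per week, 64 per arm, d = 0.5:

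| R² | Power, omitted | Power, included | Points given up | Type I error, omitted |
|---|---|---|---|---|
| 0 | 80.7% | 80.7% | 0 | 0.050 |
| 2% | 81.0% | 81.5% | 0.5 | 0.048 |
| 5% | 81.3% | 82.7% | 1.3 | 0.044 |
| 10% | 82.0% | 84.6% | 2.6 | 0.039 |

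Other cases at R² = 10%:

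- 56 per arm: nc = 0.5 × √28 = 2.646; 76.5% versus 79.6%, a loss of 3.1 points.
- 80 per arm: 89.8% versus 91.5%, a loss of 1.8 points before rounding.
- HDD per week, 64 per arm, d = 0.27: nc = 1.527; 32.4% versus 36.3%, a loss of 3.9 points from a base near 33%.

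**Step 3: check by simulation.** Permuted blocks of 4 in four strata, 160 randomised, 128 analysed, linear model with and without the strata, 6,000 runs per setting. Power without and with the strata was 79.9% and 79.5% at R² = 0, 80.5% and 81.6% at 5%, and 81.4% and 84.4% at 10%. Type I error without the strata was 0.051, 0.046 and 0.038. In a second simulation of 20,000 runs, with 20% random dropout, equal sites, 30% on psychotropics and the strata variance split equally, the mean estimate was 0.50 in every setting.

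**Step 4: what a 10% share requires.** With that split each factor carries 5%. For equal sites, δ² × 0.25 = 0.05 gives δ = 0.45 SD. For 30% on psychotropics, δ² × 0.21 = 0.05 gives δ = 0.49 SD. Overlap with HDD reduces the share that counts. If HDD explains 20% of the outcome, the strata explain 10% before adjustment, and the strata explain 5% of HDD, the joint R² is 0.2492 and the residual share is (0.2492 − 0.20)/0.80 = 6.2%.

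**Step 5: PSNHDD in the civilian trial alone.** This model has no HDD term, so R² is here the strata's share on the latent logit scale. N = 160 (dropouts count as relapsed, Section 6.K.3), model with group and sex, 5,000 runs per setting. At shares of 0, 2, 5 and 10% the power given up was 0.1, 0.4, 0.9 and 1.6 points. The odds ratio conditional on strata was 2.79, 2.83, 2.91 and 3.04, against a marginal (0.60/0.40)/(0.35/0.65) = 2.79. The standardised risk difference stayed at 0.25.

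**The case against.** The strongest reply is that stratification was meant to balance the arms, and it does so without model terms. The only loss is efficiency, and it may be nil. The 10% share needs each factor to have an effect close to the assumed drug effect, and Section 6.C already excludes medicines likely to affect drinking markedly. All of this stands, and it keeps the point minor. The plan to explore site differences shows that site is not ignored, but it adds no model term and says nothing about psychotropic use.

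A second reply concerns PSNHDD, and it also stands. Civilian/veteran status can vary only in the pooled sample that Section 6.K.7 contemplates. Section 6.B lists four sites across the two trials, and any veterans enrolled at VCU IDAS would be there for the translational components only. For trial outcomes, site therefore determines civilian/veteran status, and entering both would be redundant. A two-degree-of-freedom fix does not carry over to that analysis.

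A reader might infer that omitting the strata biases the treatment effect or inflates the type I error. The documents and the calculation do not support this: the linear estimate is unbiased and the error rate is at or below 0.05. A reader might also infer that the power figures checked in Step 1 are wrong, but they reproduce. Nor does the site label, which names Yale where Specific Aim 1 and Section 6.B name VCU IDAS, show that the wrong strata were used. It shows only that the text needs reconciling.

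**Conclusion.** The omission from the primary and continuous secondary models is certain from the text. Its effect is conditional and small. If the strata predict nothing beyond past-month HDD, nothing is lost. Otherwise the test is slightly conservative, by the amounts in Step 2.

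The range rests on the assumed cap of 10% on R². At 64 per arm and d = 0.5 the loss would be 3.9 points at 15% and 5.1 at 20%. It should not be read as covering every outcome: HDD per week exceeds it if 0.27 is standardised, and the documents give no effect sizes from which to compute GGTP, craving or alcohol-related problems. The calculation treats the primary analysis as a comparison of 8-week means, which fits the main effect of group that Section 6.K.7 powers. A stratum effect constant over time would matter little for the group-by-week test.

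For PSNHDD in the civilian trial, leaving the strata out gives an odds ratio closer to 1 than the conditional one. That is a different estimand, not an invalid test. Overall this is an improvement worth considering, not a flaw that threatens the trial's conclusions.

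**What to change.** - **Site label first.** Reconcile the site levels in Section 6.E.4 with Specific Aim 1 and Section 6.B, and confirm against the randomisation list which levels were used.
- **Primary and continuous secondary models, civilian trial.** Add site and antidepressant/psychotropic use, as recorded at randomisation, as fixed effects.
- **PSNHDD, civilian trial alone.** Add the same two factors, drop civilian/veteran status because it does not vary, and state that the odds ratio is conditional on the strata. A standardised risk difference can be reported beside it.
- **PSNHDD, pooled civilian-veteran analysis.** Use site in place of civilian/veteran status, and add psychotropic use only if both trials hold it. The veteran trial's stratification factors are not in these documents.

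The cost is two degrees of freedom in the civilian models (more in a pooled four-site model), a few sentences of analysis-plan text and one check of the randomisation list. No new data are needed for the civilian trial. If the strata are not prognostic, almost nothing is lost: in the Step 3 simulation at R² = 0, power with and without them differed by 0.4 points.

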Specific Aim 1) To evaluate fully the efficacy of and scope of effectiveness for ZNS in treating AUDs by adding a civilian arm (*N*=160 randomized, 80 on ZNS and 80 on placebo) to the CSR&D-funded study in veterans, using the same primary outcome (drinks per week) and secondary measures of drinking behavior as the veteran arm [i.e., heavy drinking days/week, percentage of subjects with no heavy drinking days (PSNHDD), craving, reductions in GGT]. Subjects will meet criteria for an AUD (DSM-5) and be heavy drinkers similar to the participants in the VA study. We hypothesize that ZNS will produce a significantly greater reduction in drinks per week than placebo (primary outcome alpha = .05). We also hypothesize that ZNS will significantly improve secondary measures of drinking (corrected for multiple comparisons). We will recruit civilians from the University of Connecticut Health Center (UCHC) and VCU's Institute for Drug and Alcohol Studies (IDAS)

Specific Aim 2) To use telephone-based daily process data collection to elucidate the mechanism of action of ZNS as it relates to changes in craving, anxiety, and genetic variation. This method has been shown to elucidate the mechanism of action of topiramate, as well as its pharmacogenetic interactions. We hypothesize that ZNS' effects will be moderated by genetic variation, craving, and anxiety, but mediated through changes in self-efficacy to reduce heavy drinking.

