AUDs are highly prevalent in civilians and in veterans, and the prevalence may be increasing over time, at least for civilians. ZNS is an extremely promising medicine for treating AUDs and managing other clinical problems including psychiatric disorders. ZNS is an affordable, generic anticonvulsant with unique actions on the major neurotransmitter systems

V.6 05Jun2020 4

involved in alcoholism, and it has neuroprotective effects. We completed a randomized, placebo-controlled pilot study of ZNS in treating AD that showed significant reductions in heavy drinking, overall drinking, and alcohol craving. ZNS was very well tolerated in this study. In this application, we propose a larger (N = 160), 16-week, randomized, double-blind, placebo-controlled, efficacy study of ZNS in reducing drinking and improving outcomes in a representative population of heavy-drinking civilians with AUD.

6. RESEARCH PLAN/EXPERIMENTAL METHODS:

6.A. CLINICAL TRIAL METHODS OVERVIEW: Overall trial design: ZNS treatment of civilians with AUD: The proposed study, which is registered on clinicaltrials.gov (NCT02900352), will be a two-arm, parallel-groups comparison of ZNS and PLC on outcomes of reducing and eliminating heavy drinking in subjects with AUD. We will conduct a 16 week, randomized, double-blind, placebo-controlled study in N=160 regularly heavy drinking subjects with DSM-5 AUD. We will enroll patients whose goal is to reduce their drinking to safe levels or to stop drinking. At each visit, all patients will receive Medical Management [47], which was developed for the COMBINE Trial and which we modified to be relevant for both reducing heavy drinking and promoting abstinence. Random assignment to treatment group and double-blind conditions will be maintained throughout the study. Raters will be trained in the reliable use of all assessments. We will use serum GGTP, Phosphatidyl Ethanol (PEth), Ethyl Glucuronide, and Ethyl Sulfate (EtS) to validate patient reports. Following a 1-2 week pre-treatment assessment period, patients will receive 16 weeks of treatment. Daily reports obtained using IVR will be used to identify subjective correlates of medication effects (e.g., craving) and to monitor medication use. A half-day long "stress response" laboratory session based on that developed by Sinha [48] will be performed with subjects after screening but before starting medication (baseline stress/impulsivity), and then a second lab will be performed between weeks 9-16.

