- d. Drinking motives and expected alcohol effects: 1) Drinking Motives: Drinking motives will be measured with the Drinking Motives Questionnaire [DMQ;[61, 62] to explore potential changes as a result of treatment in drinking motives. This instrument contains 20 items with 4 subscales, drink to a) cope motives (e.g., "Because it helps when you are feeling nervous or depressed"), b) conformity motives (e.g., "Because it helps me fit in"), c) enhancement motives (e.g., "Because it's fun"), and d) social motives (e.g., "Because it makes a social occasion more enjoyable"). The DMQ will be administered at baseline and for those subjects who continue to drink again at midpoint, end of treatment and at the 3-month follow-up visit. 2) Alcohol expectancies will be assessed with 24 items from the Alcohol Effects Questionnaire [AEQ:[63] probing 4 positive expectancy subscales (social and physical pleasure, aggression and power, social expressiveness, and relaxation and tension reduction) and 1 negative subscales (cognitive/physical impairment) to explore potential changes as a result of treatment with zonisamide. The AEQ will be administered at baseline and for those subjects who continue to drink again at midpoint, end of treatment and 3-month follow-up visit. 3) Self Rating of Effects of Alcohol (SRE) [64] is a widely used measure of number of drinks subjects report are needed to produce typical alcohol effects (alcohol sensitivity) during the first use of alcohol period in one's life, the past 3 months or period of heaviest use. The SRE will be administered at baseline and for those subjects who continue to drink again at end of treatment and 3-month follow-up visit.

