- 6.G.6. Areas assessed daily: We will use IVR to collect daily ratings of alcohol-related expectancies, craving, anxiety/tension, feelings of self-efficacy to reduce drinking, drinking, and medication usage. These are the same procedures used to examine genetic moderation of medication effects in the studies by [name] et al. [45, 79, 80]. Patients will be trained to use the IVR with a wallet-sized, follow-along sheet detailing each question in the IVR phone call, including answer options as a guide; this will be given to patients to assist them with the first few IVR calls. A research assistant will monitor calls to ensure that they are made daily and that any problems and questions are addressed immediately (to enhance accuracy and adherence). Patients who fail to call in during the allotted time receive a computerized reminder call [which has been found to increase the response rate by nearly 10% [81]]. Patients are paid \$2 for each telephone call completed and an additional \$6 for each week in which they complete 6 or more of the calls (i.e., up to \$20 per week for 16 weeks or a maximum of \$320). The use of a modest incentive helped achieve a call completion rate of 81.6% in a study of NTX [79] and 83.5% in a study of topiramate [15].
- a. Daily subjective measures assessed with IVR: These include 4 items assessing anticipated positive outcomes for drinking later that day. The items, adapted from existing expectancy scales (67-69), correspond to the commonly identified expectancy domains of general pleasure, tension reduction, social expressiveness, and enhanced sexuality. Responses will be made on a 4-point scale (0=not at all to 4=extremely likely). Similarly, subjects will report on their craving, self-efficacy for controlling drinking, and anxiety levels.

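### The drinking-motive and alcohol-expectancy scales are collected to show change due to treatment, but after baseline only patients who still drink receive them, so such change cannot be read as an effect of zonisamide.

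*Combined protocol and SAP*

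**What the plan says.** Section 6.G.5.d states a causal purpose for both scales. The DMQ is there "to explore potential changes as a result of treatment in drinking motives" and the AEQ "to explore potential changes as a result of treatment with zonisamide".

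Both are given to everyone at baseline and then restricted. For the DMQ: "The DMQ will be administered at baseline and for those subjects who continue to drink again at midpoint, end of treatment". Its later follow-up assessment is limited in the same way. For the AEQ: "The AEQ will be administered at baseline and for those subjects who continue to drink again at midpoint". The two later AEQ assessments carry the same limit. No definition or time window says who counts as continuing to drink.

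The Self Rating of Effects of Alcohol has the same gate ("The SRE will be administered at baseline and for those subjects who continue to drink again at end of treatment"), but no purpose tied to change from treatment is stated for it, so it is left out of this point.

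Two other statements show that treatment can move the gate. Section 6.A says "We will enroll patients whose goal is to reduce their drinking to safe levels or to stop drinking", and Specific Aim 1 hypothesises that "ZNS will produce a significantly greater reduction in drinks per week than placebo".

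Section 6.K mentions neither scale. Section 6.K.3 deals with dropout and missing data in general, not with scores withheld by design from abstinent patients. Section 6.E.4 asks all patients to complete every scheduled assessment in support of intent-to-treat analysis. Table 2 appears to schedule both scales at baseline and weeks 9, 16 and 28 without a drinkers-only note, though the table is damaged in the text available.

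**The concern.** Being asked the questions after baseline depends on a variable measured after randomisation that the drug is intended to change. If zonisamide works, more patients leave the assessed group on zonisamide than on placebo. The remaining drinkers in the two arms are then not the groups that were randomised, and their scores can differ even if the drug does nothing to motives or expectancies. A before-and-after change within one arm is selected in the same way, because the patients who stopped are absent from the later mean.

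At stake is the use that 6.G.5.d itself names. If lower positive expectancies go with stopping, a real fall on zonisamide looks smaller than it is, and a drug with no effect on them can appear to raise them. Scores that were never collected cannot be recovered at analysis.

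**Working it through.** **1. Plan figures.** No sample size, power or abstinence rate is given for the DMQ or AEQ. The nearest figure is in 6.K.7: over 89% power for 60% against 35% with no heavy drinking, 80 per group, two-sided 0.05. The two-proportion formula gives 0.894, so it reproduces. It supplies only a rough upper reference for abstinence.

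**2. Model (assumed).** Each patient has a standard normal tendency to keep drinking. The lowest share *a* in an arm is abstinent and not assessed. The scale score has SD 1 and within-arm correlation ρ with that tendency.

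- Shift in the assessed patients' mean within an arm: ρ·λ(a), where λ(a) = φ(z_a)/(1−a) and z_a = Φ⁻¹(a).
- Spurious difference, zonisamide minus placebo: D = ρ·[λ(a_Z) − λ(a_P)].

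**3. Inputs.** All are assumptions: a_P = 10-15%, a_Z = 20-35%, ρ = 0.3-0.5.

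| a | φ(z_a) | λ(a) |
|---|---|---|
| 0.10 | 0.1755 | 0.1950 |
| 0.15 | 0.2332 | 0.2743 |
| 0.20 | 0.2800 | 0.3500 |
| 0.35 | 0.3704 | 0.5698 |

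**4. Range with no true effect.**

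- Smallest (20% vs 15%, ρ = 0.3): D = 0.3 × (0.3500 − 0.2743) = 0.023 SD.
- Largest (35% vs 10%, ρ = 0.5): D = 0.5 × (0.5698 − 0.1950) = 0.187 SD.

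As a share of a true fall of 0.30 SD: 0.0227/0.30 = 8% and 0.1874/0.30 = 62%. The fall would appear as 0.28 SD and 0.11 SD.

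**5. Against sampling error.** In the largest case, 80 × 0.65 = 52 and 80 × 0.90 = 72 patients are assessed, before dropout. The variance in an arm is 1 + ρ²(z_aλ − λ²), which gives 0.864 and 0.928. The standard error is √(0.864/52 + 0.928/72) = 0.172 SD, so the bias is 0.187/0.172 = 1.09 standard errors. The chance of a false difference at a nominal 5% is 1 − Φ(1.96 − 1.09) + Φ(−1.96 − 1.09) ≈ 19%. The same steps for the smallest case (64 and 68 assessed, standard error 0.171) give about 5.2%.

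**6. Outside that range.**

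- Abstinence 10% vs 5%, where λ(0.05) = 0.1086: D = 0.026 to 0.043 SD for ρ = 0.3 to 0.5.
- If every patient without heavy drinking were abstinent (60% vs 35%), where λ(0.60) = 0.9659: D = 0.119 to 0.198 SD, with 32 and 52 assessed.
- Equal abstinence in both arms, or ρ = 0: D = 0.

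**7. Within one arm.** The mean change is shifted by ρ·λ(a), from 0.3 × 0.1950 = 0.06 SD to 0.5 × 0.5698 = 0.28 SD over the inputs in step 3. Equal abstinence between arms does not remove this shift.

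**The case against.** **These scales are peripheral.** A reader might infer that the mechanism aim is compromised. The documents do not support that. Section 6.K.4 works with craving, anxiety, self-efficacy and the genetic score, and self-efficacy is the mediator. The DMQ and AEQ appear in no aim and in no primary or secondary outcome. This stands in full.

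**No comparison is written out.** The plan states no contrast, model or test for either scale, so it cannot be said to have specified a biased test. This also stands. The comparison is inferred from the causal purpose stated in a two-arm randomised trial. Reading change within an arm instead does not escape the selection.

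**Best responders may still be measured.** A reader might infer that they are never assessed after baseline. The gate applies at each visit, so a patient abstinent at week 9 who is drinking by week 16 or follow-up is assessed then. Only patients classed as not drinking at all three visits are missed altogether, and without a definition their number is unknown.

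**Expectancies are also collected daily.** Section 6.G.6 says "We will use IVR to collect daily ratings of alcohol-related expectancies", with no drinkers-only condition and with domains that overlap the AEQ. This helps in part. The items are fewer, the calls are planned for the 16 treatment weeks and not follow-up, and 6.K.4 does not model them. It also shows that expectancies can be asked without a drinking condition.

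**DMQ items are reasons for drinking.** They may not suit an abstinent patient. This is fair, and for the DMQ it leaves a matter of definition and labelling.

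**Conclusion.** The point holds for the two exploratory scales. As 6.G.5.d is written, change on the DMQ or AEQ after baseline is observed in a group selected by treatment response and cannot be read as an effect of zonisamide. Nothing in 6.K repairs this, and the gate sits awkwardly with the instruction in 6.E.4 that all patients complete all assessments. The efficacy, secondary-outcome and Aim 2 conclusions do not depend on it.

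The size is not known. The 0.02-0.19 SD range rests on assumed abstinence rates and correlations and on a normal selection model. It shrinks if abstinence is rare or similar between arms. The stated direction, towards understating a fall, applies to a positive-expectancy score. The AEQ also has a negative subscale (impairment), which may shift the other way, so one should not infer that every AEQ result is biased in the same direction. This is a cheap improvement to an exploratory measure.

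**What to change.** In 6.G.5.d, give the AEQ to all patients at midpoint, week 16 and the 3-month follow-up regardless of drinking status. Compare arms on all randomised patients with data, and handle dropout as 6.K.3 already provides.

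If the DMQ stays limited to drinkers, define continuing to drink with a time window before each visit, report the number assessed by arm and visit, and present the results as describing continuing drinkers. Remove the wording that attributes DMQ change to treatment. Align Table 2 and 6.E.4 with whichever rule is kept.

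The cost is a short text change and a 24-item form for abstinent patients at visits they already attend. There is one limit. Section 6.H describes the zonisamide sample as about halfway through the trial. For patients who have passed these visits, the missing scores cannot be recovered, and mixing the two collection rules would blur the comparison. AEQ data gathered under the old rule should be reported as descriptive.
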